### **21.0** Provisions to Monitor the Data to Ensure the Safety of Subjects

21.1 Describe:

- All data collected on subjects who receive study drug will be analyzed for safety. The proportion of patients with specific adverse events will be reported as well as the worst grade observed across all adverse events. The maximum confidence interval width for these estimates is 16.8%. If the observed estimated adverse event proportion is 10%, the 95% confidence interval is (5.3, 15.6%).
- Safety information will be collected at the time of study visit when the patient is monitored during contrast administration.
- Safety data collection will begin with the first participant and participants will be monitored in real time.

- The PI or an assigned co-investigator will be responsible for monitoring the data.
- Cumulative data will be reviewed on a weekly basis beginning with the first study participant.
- All data collected on subjects who receive study drug will be analyzed for safety. The proportion of patients with specific adverse events will be reported as well as the worst grade observed across all adverse events. The maximum confidence interval width for these estimates is 16.8%. If the observed estimated adverse event proportion is 10%, the 95% confidence interval is (5.3, 15.6%).
- Any adverse event resulting from the contrast agent requiring an ICU admission will trigger an immediate suspension of the research.

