# **13.0** Local Number of Subjects

13.1 We anticipate enrolling 80 subjects.

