# 29.0 Multi-Site Research

*29.1* Study-Wide Number of Subjects: 80

29.2 Study-Wide Recruitment Methods: CMH will be the only site recruiting subjects. The University of Washington – Seattle's involvement is to provide imaging consulting. [name] will have access to our PACS system for evaluation of the imaging for analysis and image protocol validation.

- All required approvals (initial, continuing review and modifications) will be submitted to CMH IRB (IRB of record) for approval and letter of correspondence provided by CMH IRB will be sent to each site for local IRB (relying IRB) approval. Each site will be required to send documentation of local IRB approval.
- All modifications will be communicated to sites and approved (including approval by the site's IRB of record) before the modification is implemented.
- All engaged participating sites will safeguard data, including secure transmission of data, as required by local information security policies.
- All local site investigators conduct the study in accordance with applicable federal regulations and local laws.
- All non-compliance with the study protocol or applicable requirements and any unanticipated problems will be reported in accordance with local policy.
- *29.3* Describe the method for communicating to engaged participating sites:
  - All education and training to researchers and research staff will be provided by CMH and documentation of training will be recorded.
  - All reportable events must be communicated within 5 business days of notification of reportable event to CMH study staff for submission to CMH IRB (IRB of record).
  - Interim results will be communicated through virtual meetings and electronic communication as they become available.
  - The closure of a study will be communicated through electronic documentation of correspondence letter from IRB of record to participating sites for relying IRB documentation.
  - •

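### The safety precision stated in section 21.1 fits about 130 to 146 patients, not the 80 planned

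*Protocol*

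**What the plan says.** Section 21.1 of the protocol contains the same safety bullet twice. The analysis set is everyone given the contrast agent: "All data collected on subjects who receive study drug will be analyzed for safety". The unit is the patient: "The proportion of patients with specific adverse events will be reported". Two precision figures follow: "The maximum confidence interval width for these estimates is 16.8" per cent, and "If the observed estimated adverse event proportion is 10%, the 95% confidence interval is (5.3, 15.6"%). Neither a sample size nor an interval method is named.

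The sample size is given elsewhere. Section 13.1 says "We anticipate enrolling 80 subjects", section 29.1 says "Study-Wide Number of Subjects: 80", and the study summary also gives 80. Section 29.2 adds that "CMH will be the only site recruiting subjects". The only other total is 245, in the power paragraph of section 28.1.

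**The concern.** The two figures are presented as properties of this study's own estimates, yet they look too narrow for 80 patients. The familiar worst-case width for a proportion at that size is about 22 points, not 17.

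This is the protocol's only statement of how precisely the study itself will estimate harm. The reaction table in section 17.1 is background on the agent. Participants receive repeated contrast injections, most of them are children, and section 19.0 selects the category above minimal risk without prospect of direct benefit. The IRB weighing that category is told that an observed 10% would be compatible with a true rate up to 15.6%. If the correct limit is higher, the error is in the favourable direction.

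**Working it through.** **Inputs.** N = 80 (summary, sections 13.1 and 29.1). Confidence level 95%, z = 1.96 (section 21.1 states it for the 10% example; I assume the same for the maximum width). The denominator is patients who receive the agent, so 80 is the most it can be under the planned enrolment. Weekly repeat examinations do not enlarge it.

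**Step 1: try to reproduce the stated figures at N = 80.** The width is largest at p = 0.5.

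- Wald maximum width: 2 × 1.96 × √(0.25/80) = 3.92 × 0.0559 = 21.9 points.
- Wilson maximum width: 3.92 × √(0.25/80 + 1.96²/(4 × 80²)) / (1 + 1.96²/80) = 3.92 × 0.0572 / 1.048 = 21.4 points.
- Exact (Clopper-Pearson) maximum width, at 40/80: 22.8 points.
- Wald interval at 8/80: 0.10 ± 1.96 × √(0.09/80) = 0.10 ± 0.066, which is 3.4 to 16.6%.

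| Method, N = 80 | Maximum width | 95% CI at 8/80 |
|---|---|---|
| Stated in section 21.1 | 16.8 | 5.3 to 15.6% |
| Wald | 21.9 | 3.4 to 16.6% |
| Wilson | 21.4 | 5.2 to 18.5% |
| Jeffreys | 21.6 | 4.8 to 18.0% |
| Exact | 22.8 | 4.4 to 18.8% |

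Adding the Agresti-Coull, mid-P, uniform-prior and continuity-corrected intervals, the maximum width runs from 21.4 to 23.2 and the upper limit at 10% from 16.6 to 19.3%. Wilson comes close to the stated lower limit but not to the upper. Neither stated figure is reproduced.

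**Step 2: look for a reading that rescues them at N = 80.**

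- At 90% confidence the maximum width is 18.1 to 19.6, and at 80% it is 14.1 to 15.6.
- If 16.8 were a half-width, it should be compared with 10.7 to 11.6.

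None of these gives 16.8.

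**Step 3: solve for N.**

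- Wald, maximum width 16.8: n = 0.25 × (3.92/0.168)² = 136.
- Wilson needs 132 to 133. Exact needs 145 to 146.
- The stated interval is 15.6 − 5.3 = 10.3 points wide. Wald at 10%: n = 0.09 × (3.92/0.103)² = about 130.
- The stated interval is not symmetric about 10% (4.7 below, 5.6 above), so it is not a Wald interval at exactly 10%.
- The exact method at n = 146 matches both figures: its maximum width is 16.8, and 14/146 (9.6%, which rounds to 10%) gives 5.34 to 15.57%.

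**Step 4: check the other total in the protocol.** At N = 245 the maximum width is 12.4 to 12.9, so 245 is not the source.

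**The case against.** The arithmetic cannot be defended, so the case on the other side is about weight and remedy.

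- *Nothing depends on the interval.* The sample size rests on the elastography comparison, no objective concerns adverse event rates, and neither the weekly safety review nor the suspension trigger uses it. The final intervals will be computed from the data observed. This is true, and it means that correcting the text changes no procedure. It does not make the statement right, and the statement is part of what the IRB reads when it judges the risk.
- *The 10% is hypothetical, and the protocol sets no rate to exclude.* Also true. The error is in the precision claimed, not in a test or a decision threshold.
- *The implied N is not unique.* It varies with the method, and the interval 5.3 to 15.6% was found only at proportions near 10%, not at exactly 10%. That the text was written for a study of about 146 patients is an inference. The mismatch with 80 does not depend on it.
- *The planned N is itself in conflict.* Section 28.1 says 245 are needed and mentions other sites. This stands as a reason to tie the correction to the reconciled number, but 245 does not support the stated figures either.

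**Conclusion.** The concern holds. For 80 patients the maximum 95% width is understated by 4.6 points (Wilson, 21.4 − 16.8) to 6.0 points (exact, 22.8 − 16.8). The upper limit at an observed 10% is understated by 1.0 point (Wald, 16.6 − 15.6) to 3.2 points (exact, 18.8 − 15.6).

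The same loss of precision applies when no event is seen. The exact two-sided upper limit, 1 − 0.025^(1/n), is 4.5% for n = 80 and 2.5% for n = 146.

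The conclusion assumes that the maximum width is a full width at the 95% level, as the adjacent sentence suggests, and that all 80 patients receive the agent. If fewer do, the true precision is worse still.

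**What to change.** Settle the number of patients expected to receive Lumason, reconciling the 80 with the 245 in section 28.1. Then replace the precision sentences in both bullets of section 21.1, naming N and the interval method. For 80 recipients the text could read: *With 80 patients, the maximum width of the exact (Clopper-Pearson) 95% confidence interval is 22.8 percentage points; for 8/80 (10%) the interval is 4.4 to 18.8%.* If fewer than 80 will receive the agent, compute both figures for that number. Since the two bullets are identical, one could be deleted.

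The cost is two sentences of wording. Design, procedures and analysis do not change, but the stated precision becomes less favourable and the IRB should see the corrected figures.

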### **17.0** Risks to Subjects

17.1 We do not anticipate any additional risks to this study as all patients will already have IV access per SOC for BMT and no additional line placements will be required as part of this study. All subjects will be monitored during the Lumason CEUS examination by radiology personnel and by BMT staff after the exam for any adverse events.

Reported risks related to Lumason administration include:

Serious cardiopulmonary reactions, including fatalities, have occurred uncommonly in adults during or shortly following administration of ultrasound contrast agents, including Lumason. These reactions typically occurred within 30 minutes of administration. Hypersensitivity reactions such as skin erythema, rash, urticaria, flushing, throat tightness, dyspnea, or anaphylactic shock have uncommonly been observed following the injection of Lumason. The exclusion criteria eliminate any subjects with a known cardiac abnormality or a known sensitivity to sulfur hexafluoride, so we do not anticipate that these reactions will occur. Resuscitation personnel and equipment will be available during the study treatment and follow-up period.

Adverse Reaction	Number	(%)
Any Adverse Reaction	340	5
Headache	65	1
Nausea	37	0.5
Dysgeusia	29	0.4
Injection site pain	23	0.3
Feeling hot	18	0.3
Chest discomfort	17	0.2
Chest pain	12	0.2
Dizziness	11	0.2
Injection site warmth	11	0.2

17.2 This study poses a minor increase over minimal risk as it does not hold the prospect of direct benefit for the individual subject, but the

intervention presents an experience that is reasonably commensurate with those inherent to the subject's medical situation and is likely to yield generalizable knowledge about the disorder which is of vital importance to the detection of VOD/SOS. Physicians will be blinded to the results of the imaging.

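### Read literally, the safety-collection rule in 21.1 covers a shorter period than the post-exam monitoring and risk period in 17.1, so delayed contrast reactions may go unrecorded

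*Protocol*

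**What the plan says.** Section 21.1 (safety monitoring) has one sentence on the timing of collection: "Safety information will be collected at the time of study visit when the patient is monitored during contrast administration". It adds that "Safety data collection will begin with the first participant and participants will be monitored in real time". The output is defined as follows: "The proportion of patients with specific adverse events will be reported as well as the worst grade observed across all adverse events".

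Section 17.1 (risks) places serious cardiopulmonary reactions during administration or shortly after it, and says "These reactions typically occurred within 30 minutes of administration". On observation it says "All subjects will be monitored during the Lumason CEUS examination by radiology personnel and by BMT staff after the exam for any adverse events". It also states that "Resuscitation personnel and equipment will be available during the study treatment and follow-up period", without giving the length of that follow-up period.

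Section 6.1 schedules contrast ultrasound before conditioning and then weekly to day +30 or discharge, and until resolution in patients with SOS. Whatever rule applies to one exam therefore applies many times per patient.

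**The concern.** Observing a patient and recording an event are different acts. Section 17.1 provides for observation after the exam. Section 21.1, taken at its word, provides for collection during contrast administration. An event first seen back on the ward may be noticed and managed clinically yet never reach the study database.

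The stake is the study's safety output. Missing delayed events can lower the adverse-event proportions and the worst grade but cannot raise them. An analysis plan cannot repair this later, because it can only summarise events that were collected. Section 19.0 classes the study as greater than minimal risk with no prospect of direct benefit to the children enrolled, which makes complete capture of contrast reactions important.

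**Working it through.** **Step 1. The two sections side by side.**

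| | Section 17.1 | Section 21.1 |
|---|---|---|
| Period | During and shortly after administration, typically within 30 minutes | Study visit, during contrast administration |
| Who | Radiology during the exam, transplant staff after it | Not stated |
| Activity | Monitoring | Collection of safety information |
| Duration after the exam | Not stated | Not mentioned |

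The period named in 21.1 is the shorter one.

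**Step 2. Does another provision close the gap?**

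- Real-time monitoring (21.1) says that participants are watched. It does not say for how long after the exam, or that ward observations are entered.
- The statement in 21.1 that all data collected on treated subjects are analysed for safety covers what has been collected. It does not widen collection.
- Section 23.1 sends adverse events resulting from the study procedure to the principal investigator and the IRB, with no time limit. That is a reporting duty for events already recognised and attributed. It does not place them in the data set behind the proportions.
- Section 6.4 extracts further clinical variables from the medical record. It names transplant outcomes, SOS criteria and liver parameters, but not contrast reactions. Its general clause is tied to the study objectives, and section 2.0 lists no safety objective.
- Section 22.3 limits REDCap access to approved study team members. No route is given from transplant staff to the database.

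None of these clearly closes the gap, and none says that post-exam events are excluded.

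**Step 3. Size.** The plan has no figure for the share of reactions that begin after administration, so there is nothing to reproduce on this point. The confidence-interval figures in 21.1 concern precision and do not bear on capture.

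Let p be the true proportion of patients with an event, and s the share of affected patients who have at least one recorded event. Then

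observed proportion = p × s.

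With n = 80 (section 13.1), and with p and s assumed:

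| s | p = 10%: observed (expected patients) | p = 5%: observed | p = 5%: chance of no event in 80 = (1 − p × s)^80 |
|---|---|---|---|
| 1 | 10.0% (8) | 5.0% | 1.7% |
| 0.9 | 9.0% (7.2) | 4.5% | 2.5% |
| 0.75 | 7.5% (6) | 3.75% | 4.7% |
| 0.5 | 5.0% (4) | 2.5% | 13.2% |
| 0.25 | 2.5% (2) | 1.25% | 36.6% |

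The first row is the case in which all post-exam events are recorded, and there the bias is zero.

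**Step 4. Reactions are not patients.** The share s counts patients. Because exams repeat, a patient with several reactions may be counted from any one of them. If each reaction is captured with probability c, independently, a patient with k reactions is captured with probability 1 − (1 − c)^k. With c = 0.5 this is 0.5 for k = 1 and 0.75 for k = 2. A given share of late reactions therefore costs the same share of patients only when each affected patient has a single reaction.

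**The case against.** The strongest reply is that 21.1 says when information is collected but not that collection ends with the injection. The study visit could be read to include the period afterwards. Transplant staff are told to watch for any adverse events, and a follow-up period is mentioned. Participants are monitored in real time, and procedure-related events go to the investigator and the IRB. Section 6.3 also refers to an attached data collection sheet that is not shown and could contain a recording window. Finally, adverse-event proportions are not among the study's objectives or endpoints.

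Much of this stands. It rules out several stronger readings that a reader might infer:

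- That safety data are collected only during the injection. The protocol does not state such a restriction, and exclusion of later events would be inferred from silence.
- That reactions occur up to 30 minutes later. Section 17.1 says typically within 30 minutes, which is not a limit. It also includes reactions during administration, and it describes uncommon events in adults.
- That the reported proportions will be too low. This follows only if post-exam events are left out, which the text does not establish.
- That the suspension rule is weakened. The rule reads "Any adverse event resulting from the contrast agent requiring an ICU admission will trigger an immediate suspension of the research". Nothing makes recognition of an ICU admission depend on the collection window in 21.1.

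The mismatch of wording remains. The one sentence that fixes collection names a shorter period than the protocol's own monitoring plan, and no provision in the document clearly links the two.

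**Conclusion.** The point holds as a misalignment to be reconciled. Sections 17.1 and 21.1 describe different periods, and followed literally 21.1 may leave delayed reactions out of the safety data set. The reported proportions and worst grade may then be too low.

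The direction of this error is certain if events are lost, but whether any are lost is not. The documents do not allow its size to be computed: it is zero if post-exam events are recorded. The figures in the working rest on assumed values of p and s and are not estimates of what will happen in this study. The change is worth making because it is cheap and because events not recorded at the time may not be recoverable.

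**What to change.** Reconcile the two sections. State in 21.1 that adverse events observed by radiology personnel and by transplant staff, during the post-exam monitoring that 17.1 describes, are recorded in the safety data set after every contrast exam. Use one recording window in both sections, covering the risk period that 17.1 itself cites. Name the route by which transplant staff observations reach REDCap, and record the time of onset relative to administration, so that the timing split missing today becomes known.

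This concerns recording. How patients are monitored clinically is for the investigators. The cost is a short change to 21.1 with matching wording in 17.1, a time field in REDCap, and a small amount of extra data entry per exam, since the observation is already planned.

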### 3.0 Background

3.1 Hepatic sinusoidal obstructive syndrome (SOS) is a complication of blood and marrow transplant (BMT) that is associated with high morbidity and mortality. 57,000 patients in the United States and Europe undergo BMT annually (1, 2), and SOS affects up to 15% of these patients (3). SOS pathogenesis is thought to be caused by damage to the hepatic venous endothelium due to the preparative regimen used before BMT. This damage results in obstruction of blood flow through the liver. Pathology shows collagen deposition in the sinusoids and fibrosis of venous lumens (10). The severity of the disease is correlated to the number and severity of the histological changes. Mild and moderate SOS can resolve with supportive treatment. Severe SOS (30% of SOS) is commonly associated with multi-organ failure and has a mortality rate of 80% despite available prophylaxis and treatment (Table 1) (4).

Table 1. Staging of VOD/SOS	Table 1.	Staging	of VOD/SOS 
-----------------------------	----------	---------	--------------------------

Mild : Resolved without interventions	
Moderate : Requires treatment	
• Bilirubin $> 6 \text{ mg/dl}$	
• AST > 5 times upper limit of normal	
• Weight gain $> 5\%$	
• Ascites	
Severe : Progression to Multi-organ dysfunction syndrome	

 
Respiratory failure (O2 saturation < 90 %)
 
	
Hepato renal syndrome	
• Encephalopathy	

- Severe renal failure ( creatinine > x 2)
- Bilirubin > 20 mg/ dl

SOS is most commonly defined by two clinical criteria: the modified Seattle criteria and the Baltimore criteria (Table 2) (11, 12). The modified Seattle criteria state that at least two of the following criteria must be present within 20 days of BMT: bilirubin  $\geq 2mg/dL$ ; hepatomegaly and/or ascites; and/or weight gain  $\geq 5\%$  above baseline weight (11). Pediatric SOS incidence in BMT is 20% and is higher compared to adults (13-15). Death or multi-organ dysfunction affects 30-60% children who develop SOS (16, 17). The most common definition of severe SOS is retrospective, namely death from SOS-related causes or persistent multi-organ dysfunction at 100 days post BMT. However, the European Society for Blood and Marrow Transplantation has proposed a new prospective SOS grading scheme that will likely become standard of care since it is pediatric patient specific and it is can be performed prospectively and thus can guide treatment (5).

Modified Seattle Criteria	Baltimore Criteria

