3.3 The long-term goal of our research is to accurately identify SOS patients who would benefit from defibrotide treatment using US SWE. The overall objective of this study is to validate SWE as an early diagnostic marker for SOS. Our central hypothesis is that SWE changes will precede clinical and conventional US diagnostic criteria for SOS. Our hypothesis has been formulated on the basis of our own preliminary data. We completed the first prospective cohort trial demonstrating that US SWE provides SOS diagnosis (80% sensitivity and 67% specificity) nine days earlier than current clinical criteria (9). SWE is widely available, has no known side effects, and is easy to learn and interpret. Our study enrolled 25 high-risk BMT patients over 18 months (five with SOS and two with severe SOS). More data is needed to determine the optimal window for testing to balance between improved test characteristics and early detection of disease. We propose conducting a prospective cohort study with 80 additional patients, 12 of which will likely develop SOS (including four with severe SOS) to optimize SWE timing. This study will increase the confidence in the findings from our preliminary study and allow us to test SWE against newly published clinical criteria. The rationale for the proposed research is that, if SWE can diagnose SOS earlier than clinical criteria, then SWE can guide early initiation of SOS treatment.

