### Ultrasound Examinations and Timeline

After enrollment and within two weeks prior to starting their conditioning regimen, a limited abdominal US with Doppler measurements of the hepatic arteries, hepatic and portal veins, contrast enhanced ultrasound (CEUS) of the liver, as well as SWE will be performed.

Subjects will be undergo US examinations based on disease course as outlined below:

- 1. All Patients: Patients will undergo limited abdominal US with Doppler, CEUS and SWE once a week upon admission for conditioning until the patient day +30 BMT or discharge, whichever comes first.
- 2. Inpatient SOS: patients will undergo limited abdominal US with Doppler, CEUS and SWE once a week upon admission for conditioning until resolution of SOS.
- 3. Late Onset SOS: patients will undergo limited abdominal US with Doppler, CEUS and SWE once a week upon admission for conditioning until resolution of SOS.

The clinical team will order US, CEUS and SWE exams when patients have clinical suspicion for SOS and we will include these exams in our analysis. All imaging will be performed using GE Logiq E9 US machines by dedicated pediatric sonographers and interpreted by board-certified pediatric radiologists. Twelve shear wave velocity measurements will be taken 2-3 cm below the liver capsule at the mid-clavicular line in the right hepatic lobe and another 12 will be taken in the left hepatic lobe near midline

avoiding areas of vasculature (24). By necessity, the sonographer and interpreting radiologist will not be blinded to the clinical status of the patient. US and clinical data will be collected weekly and managed using REDCap electronic data capture tools hosted at Children's Mercy Hospital (25).

	ALL PATIENTS		INPATIENT SOS	LATE ONSET SOS
	Prior to	Start of Conditioning	Through	Through Resolution of
	Conditioning	through Day +30	Resolution of SOS	SOS
	Screening	Once per Week	Once per Week	Once per Week
Limited Abdomen and Limited Abdominal Doppler Ultrasound	X	Х	Х	X
Contrast Enhanced Ultrasound	X	X	X	X
Ultrasound Elastography	X	X	X	X

Table 3. Ultrasound Timeline

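### The protocol's only automatic suspension rule (21.1) turns on ICU admission rather than severity, so read literally it omits a contrast-related death before transfer and a life-threatening reaction in a patient already in the ICU

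*Protocol*

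**What the plan says.** Section 21.1 gives one event that stops the study without further judgement: "Any adverse event resulting from the contrast agent requiring an ICU admission will trigger an immediate suspension of the research". No other section states a suspension or stopping criterion.

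Section 17.1 describes the risk that the rule is there to catch: "Serious cardiopulmonary reactions, including fatalities, have occurred uncommonly in adults during or shortly following administration of ultrasound contrast agents, including Lumason". It adds that these reactions usually came within 30 minutes of the injection.

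For both inpatient and late-onset SOS, section 6.1 (Ultrasound Examinations and Timeline) says that "patients will undergo limited abdominal US with Doppler, CEUS and SWE once a week upon admission for conditioning until resolution of SOS". Section 3.1 describes the sickest of these patients: "Severe SOS (30% of SOS) is commonly associated with multi-organ failure and has a mortality rate of 80% despite available prophylaxis and treatment". Table 1 in that section includes respiratory failure among the features of severe disease.

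Other safety provisions surround the rule. Section 21.1 provides real-time monitoring and also says that "Cumulative data will be reviewed on a weekly basis beginning with the first study participant". Section 17.1 says that "Resuscitation personnel and equipment will be available during the study treatment and follow-up period". Section 16.1 lets the treating physician withdraw a patient. Section 23.1 sends adverse events from the study procedure to the principal investigator and the IRB, to be handled under institutional policy. Section 29.3 sets a limit of 5 business days for passing on reportable events.

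**The concern.** An automatic halt rule exists so that nobody has to decide, in the middle of an event, whether the study should stop. This one is tied to a change of location. A reaction that moves a ward patient to intensive care stops the study at once. For a reaction that kills the patient before transfer, or that threatens the life of a patient already in intensive care, the sentence taken at its word requires nothing, although the event is as serious or worse.

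The wording matters more here because sections 18.1 and 19.0 state that the study offers participants no direct benefit and place it in pediatric risk Category 3. Children receive repeated contrast injections for research, so the condition for stopping should be unambiguous.

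**Working it through.** The rule is verbal, with no threshold, count or error rate to reproduce. The check is to apply it to the serious events that the protocol itself makes conceivable.

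**Step 1. Two readings of the trigger.** The literal reading asks whether the event led to, or called for, a transfer into the ICU. The severity reading asks whether the event was grave enough to need intensive care.

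| Contrast-related event | Literal reading | Severity reading |
|---|---|---|
| Ward patient transferred to the ICU | Suspends | Suspends |
| Patient transferred to the ICU who then dies | Suspends (at transfer) | Suspends |
| Patient dies before any transfer | Not required | Suspends |
| Life-threatening reaction, patient already in the ICU | Not required | Suspends |

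The readings part on the last two rows only.

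**Step 2. Can those two rows arise?** Death before transfer: section 17.1 names fatalities and a typical onset within 30 minutes, so a death in radiology or on the ward is possible. Section 17.1 does not expect such reactions, because it says that patients with a known cardiac abnormality or sulfur hexafluoride sensitivity are excluded. The exclusion list in section 11.1 names neither and has only a general clause on medical conditions that the investigator finds unsuitable.

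Reaction in the ICU: section 6.1 makes no exception for critical illness, and section 10.1 ends participation at discharge or Day +100, not at ICU transfer. Severe SOS commonly brings multi-organ failure (3.1). A scan in a patient under intensive care is therefore plausible, but it is an inference.

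**Step 3. Does another provision supply the missing halt?** Real-time monitoring, weekly review, resuscitation cover, individual withdrawal, investigator and IRB review, and the reporting limit all apply. None states when the study must stop. The institutional policy cited in 23.1 is not shown and may do so.

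**Step 4. Size of the group in which the ICU case is most plausible.**
- Inputs: 80 patients and 12 expected SOS cases, four of them severe (3.3); 30% of SOS is severe (3.1).
- Check: 12 / 80 = 15%, the upper figure for SOS incidence in 3.1; 12 × 0.30 = 3.6, which agrees with the stated four.
- Share of the cohort: 4 / 80 = 5%.
- With the pediatric incidence of 20% also given in 3.1: 80 × 0.20 = 16 and 16 × 0.30 = 4.8, or 4.8 / 80 = 6%.

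This counts severe SOS patients. It does not count ICU stays, reactions or missed suspensions, and no rate of serious contrast reactions is given from which to go further.

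**The case against.** The strongest reply is that *requiring* sets a level of severity. A fatal reaction, or one that endangers the life of a patient already in the ICU, plainly reaches the level at which intensive care is needed, so a sensible investigator would suspend. This is a fair reading, and nothing in the protocol contradicts it. Nor does section 21.1 say that suspension is limited to this trigger. What remains is that the text names an admission, and that it leaves the two gravest cases to interpretation.

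Second, no section places a scan in the ICU. Section 17.1 has radiology personnel watching the patient during the examination and BMT staff afterwards, which fits a radiology or transplant-unit setting without ruling out the ICU. Severe SOS is also a weak proxy for intensive care, since Table 1 counts a bilirubin or creatinine threshold among its severe features. This stands, and it is why the ICU case is offered as plausible only.

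Third, a treating physician could withdraw a patient who becomes too ill (16.1), and any procedure-related event reaches the principal investigator and the IRB (23.1). This also stands. It means that oversight exists, though not that a halt is mandated.

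A reader might go further and infer that the study would carry on after a contrast-related death, or that about four ICU patients are left unprotected. The documents support neither. The first ignores the severity reading and the review under 23.1; the second takes expected severe SOS cases for ICU patients.

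**Conclusion.** The point holds as a minor defect of wording and a cheap improvement. The one automatic trigger depends on location, and on a literal reading it does not mandate suspension for a contrast-related death before transfer or for a life-threatening reaction in a patient already in the ICU. The first case rests on a risk that section 17.1 lists. The second rests on the assumption that some patients scanned weekly until SOS resolves will be in intensive care.

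The size cannot be given as a rate: section 17.1 calls serious reactions uncommon, reports them in adults, and gives no frequency for them. The conclusion is confined to the protocol's own text, because the institutional policy cited in 23.1 is not available.

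**What to change.** Replace the sentence in 21.1 with wording such as: *The research is suspended immediately after any contrast-related death, or any contrast reaction that is life-threatening or requires ICU admission, wherever the patient is when it occurs.*

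A separate trigger for escalation of ICU-level care is not advised. In multi-organ failure, new respiratory or circulatory support is often part of the disease, so attribution to contrast would be difficult, and the life-threatening criterion already catches the cases that matter.

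The cost is one sentence in an amendment and, rarely, an extra pause for review, for instance when a death is first attributed to contrast and later explained otherwise.
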